Qualitative analyses: We anticipate thematic saturation will be reached with this number (N=approximately 10-15) of participants based on previous studies (i.e., the point at which no new data emerge).^{16,17} All interviews will be conducted and audio-recorded by study personnel and then transcribed by a professional transcription service. Two trained personnel (“coders”) will extract and highlight themes from the transcripts. We will analyze the qualitative data using grounded theory and constant comparative methods, with coding to structure data into categories and create groups according to the broader issues or themes.³¹ The themes will focus on feedback on training materials (e.g., prerecorded vs. interactive sessions, duration of training) and processes (e.g., workflow, template to document ACP visit in the electronic medical record) in the inpatient setting. These interviews will be audio-recorded by study personnel and then transcribed. We will keep an audit trail to establish trustworthiness. We will critically examine the data collection and analysis process, discuss emerging codes, and reach consensus on principal themes. These themes will be used to adapt the inpatient APP/fellow-delivered ACP intervention.

[figure not shown]
8.2.2 Analysis Plan for Aim 2

Quantitative analyses: We will use descriptive statistics to summarize feasibility metrics and all measures. Feasibility will be defined based on the retention rate (% of patients approached who consented and complete the ACP visit); >70% will be considered a successful benchmark for feasibility. Rates will be presented with associated two-sided 95% exact binomial confidence

intervals. A sample size of 50 patients produces a confidence interval with a maximum width of 0.29 (limits 0.36-0.65), when the observed feasibility rate is 0.50. We anticipate a higher feasibility rate, which will result in a narrower confidence interval. If the observed feasibility rate is 0.70, the width of the confidence interval is reduced to 0.24 (limits 0.55-0.82). If more than 50 patients are approached, then the confidence intervals will become narrower. Recruitment rate will be the % of patients approached who agree to participate (i.e., consent), and will be described similarly.

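### Section 8.2.2 gives a confidence interval width of 0.24 at an observed feasibility rate of 0.70 with 50 patients, but its own limits (0.55-0.82) give 0.27

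*Combined protocol and SAP*

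**What the plan says.** Section 8.2.2 of the combined protocol and SAP sets the interval method: "Rates will be presented with associated two-sided 95% exact binomial confidence" intervals. It sets the feasibility criterion: ">70% will be considered a successful benchmark for feasibility". It then supports the sample size with two worked examples.

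- At an observed rate of 0.50: "A sample size of 50 patients produces a confidence interval with a maximum width of 0.29 (limits 0.36-0.65").
- At an observed rate of 0.70: "If the observed feasibility rate is 0.70, the width of the confidence interval is reduced to 0.24 (limits 0.55-0.82").

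The next sentence deals with larger denominators as a separate case: "If more than 50 patients are approached, then the confidence intervals will become narrower". The 0.70 example is therefore to be read at 50 patients, like the one before it.

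Section 3.7 (Number of Subjects) also discusses 50 patients, but argues only that this number can be recruited in 18 months. It makes no statement about precision.

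**The concern.** The second example contradicts itself: its stated width is 0.24, while its stated limits are 0.27 apart. One of the figures must be wrong, and the sentence alone does not show which.

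The two examples are the only statistical support the plan gives for 50 patients. If the limits were wrong, the interval at the benchmark rate would be misdescribed. If the width is wrong, the plan claims more precision at that rate than 50 patients provide. The figure could also be carried into a report or into the planning of a follow-on study.

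**Working it through.** **Inputs, all from section 8.2.2.** Two-sided 95% exact binomial interval; n = 50; observed rates 0.50 (x = 25) and 0.70 (x = 35).

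**Formula (Clopper-Pearson).** Lower limit = 2.5% quantile of Beta(x, n - x + 1). Upper limit = 97.5% quantile of Beta(x + 1, n - x).

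**Step 1: reproduce the plan's first example, 25/50.**
- Lower: Beta(25, 26) at 2.5% = 0.3553
- Upper: Beta(26, 25) at 97.5% = 0.6447
- Width: 0.2895

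The stated 0.29 reproduces, which confirms the method and n. The upper limit rounds to 0.64; the printed 0.65 is one unit off in the last digit.

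**Step 2: the second example, 35/50.**
- Lower: Beta(35, 16) at 2.5% = 0.5539
- Upper: Beta(36, 15) at 97.5% = 0.8214
- Width: 0.2675, that is, 0.27

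The printed limits reproduce. The printed width does not.

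**Step 3: could rounding explain it?** The narrowest width compatible with limits rounding to 0.55 and 0.82 is 0.815 - 0.555 = 0.26. The widest is 0.825 - 0.545 = 0.28. A width of 0.24 is excluded.

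**Step 4: could another method explain it?** Intervals for 35/50:

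| Method | Limits | Width |
|---|---|---|
| 95% exact (specified) | 0.5539-0.8214 | 0.2675 |
| 95% Wald | 0.573-0.827 | 0.254 |
| 95% Wilson | 0.5625-0.809 | 0.2465 |
| 95% Agresti-Coull | 0.5617-0.8097 | 0.248 |
| 95% Jeffreys | 0.5645-0.8131 | 0.2487 |
| 95% inverted binomial test | 0.5604-0.812 | 0.2516 |
| 95% mid-P | 0.563-0.8145 | 0.2515 |
| 90% exact | 0.5763-0.8051 | 0.2288 |

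No width rounds to 0.24, and only the specified method gives limits of 0.55 and 0.82.

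**Step 5: could a different denominator or rate explain it?** At a rate of 0.70, 60 patients give a width that rounds to 0.24 (42/60: 0.2436), but the limits are then 0.568-0.812. With 50 patients the width first rounds to 0.24 at 39/50, a rate of 0.78 (0.6404-0.8847, width 0.2443); at 38/50 it is still 0.2511. Neither case matches the printed sentence.

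**Step 6: size of the error.**
- Absolute: 0.2675 - 0.24 = 0.0275
- Relative: 0.0275 / 0.2675 = 0.103, about 10%
- Narrowing from a rate of 0.50 to 0.70: 0.2895 - 0.2675 = 0.022, against 0.29 - 0.24 = 0.05 as printed

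**The case against.** The strongest objection is that nothing depends on the figure. The right limits stand beside it, the plan sets no precision target that 0.24 meets and 0.27 misses, and feasibility is decided by the observed rate exceeding 70%. All of this is correct and is why the point is minor.

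A second objection is that the study may in fact achieve an interval narrower than 0.24. Section 8.2.2 takes patients approached as the denominator, and section 3.7 cites consent rates of 65-75% in earlier studies. If those rates applied, enrolling 50 patients would mean approaching about 50/0.75 = 67 to 50/0.65 = 77. Exact widths near a rate of 0.70 would then be 0.230 (47/67) to 0.214 (54/77). This is fair, and it confines the overstatement of precision to a denominator of 50. It does not rescue the printed figure, which illustrates 50 patients and carries the limits for 50. Section 7.2.3.11 bases retention on consented patients instead, and there a denominator of 50 would apply if exactly 50 consented.

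Finally, 35/50 is on the boundary and would not itself pass a criterion of more than 70%. That is true, but it is still the rate at which the plan chose to state its precision.

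**Conclusion.** The error is confirmed and minor. For 50 patients and an observed rate of 0.70, the specified method gives a width of 0.27, and the printed 0.24 is about 0.027 (10%) too narrow. This rests on the example being at n = 50, which the text around it and the match of both printed limits support. Where the 0.24 came from cannot be established from the document. The maximum width of 0.29 is sound, and the case for 50 patients is not materially weakened.

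**What to change.** In section 8.2.2, replace the width of 0.24 with 0.27 and leave the limits 0.55-0.82 as they are. In the same edit, change the upper limit of the 0.50 example from 0.65 to 0.64. Because 0.36 and 0.64 differ by 0.28 after rounding while the true width is 0.29, printing three decimals (0.355-0.645 and 0.554-0.821) would prevent a new apparent mismatch.

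The cost is a text correction and a slightly less favourable stated precision at 0.70. No change to sample size, benchmark or analysis follows from this point.

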ACP is a process that supports adults in understanding and sharing their personal values, life goals, and preferences regarding medical care. These decisions can then be recorded in MOLST/POLST forms to guide surrogate decisions makers if the patient loses decision making capacity. Our preliminary data demonstrates that among adults with AML and myelodysplastic syndrome (MDS) seen at the Wilmot Cancer Institute (WCI) and its affiliated community centers, most MOLST forms were completed late in the disease course.¹² Compared to patients who completed MOLST \leq 30 days prior to death or never completed MOLST, those who

completed MOLST >30 days prior to death were less likely receive inpatient care and more likely to utilize hospice at the EOL, indicating early MOLST completion is associated with better EOL care. Interventions to improve access to ACP and MOLST/POLST completion can therefore be expected to improve EOL care.

1.4. Evidence-based interventions can improve access to ACP but are not tailored to older adults with hematologic malignancies.

The Serious Illness Care Program (SICP) is an evidence-based intervention to enhance EOL conversations between physicians and patients with advanced cancer in the outpatient setting.¹³ It consists of the Serious Illness Conversation Guide (SICG) as well as training and system-level support for physicians to conduct conversations about ACP. In a phase III randomized trial, compared to the control arm, more patients and physicians in the intervention arm had serious illness conversations (96% vs. 79%) and these conversations occurred 2.4 months earlier and were more comprehensive and patient centered. However, less than 10% had hematologic malignancies. Therefore, we have adapted the SICP for older patients with hematologic malignancies based on feedback from clinicians [oncologists, palliative care physicians, advanced practice providers (APP), and nurses)], older patients with these diseases, and their caregivers.

1.5. Previous research has shown that advanced practice providers-initiated ACP discussions improve ACP engagement.

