1.6. Overall goal

The long-term goal of this proposal is to improve ACP access and EOL care in older patients with hematologic malignancies via an inpatient ACP intervention delivered by APPs and hematology/oncology trainee physicians (hereby referred to as fellows).

The objective of this two-year project is to create training materials and processes for an inpatient ACP intervention and to assess its preliminary efficacy in older patients with hematologic malignancies in a single arm study (comparing data to historical control).¹³

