3.5 Inclusion and Exclusion Criteria for Patients (Aim 2)

Inclusion criteria:

- Age \geq 60 years
- A diagnosis of hematologic malignancy [including but not limited to acute leukemia, myeloid malignancies (e.g., atypical CML, MDS/MPN overlap syndromes, CMML), multiple myeloma, lymphoma, or any other hematologic malignancies based on the primary oncologist's judgment]
- Able to provide informed consent
- Being managed in the inpatient setting
- English-speaking

Version Date: 5/10/23

PRMC#: UOCPC22039

Study Protocol

ClickIRB #: STUDY00007403

Exclusion criteria

- None

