3.9. Age of Subjects

We will recruit patients with hematologic malignancies aged 60 and above (from date of consent, confirmed on electronic medical record).

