7.2.2. Clinical and Cancer Characteristics (Patient)

ECOG performance status, comorbidities, medications, weight, height, BMI, diagnosis and date of diagnosis, prior hematologic malignancies, stage/risk group, and treatment regimen will be abstracted from the medical records. This information will only be collected at baseline.

In addition, we will collect the following from the medical records (up to 5 years following their participation in the study or death) which will provide end of life quality indicators. We have previously collected this information in a retrospective fashion and will use similar procedures to extract this information prospectively from the medical records.

- Hospice enrollment (and timing relative to death)
- Palliative care referral (and timing relative to diagnosis)
- Chemotherapy administration within the last 2 weeks of life
- Completion of advance directives which include MOLST forms, living will, durable power of attorney for healthcare, and healthcare proxy forms (and timing related to diagnosis and death)
- Do not resuscitate order /Do not intubate order (and timing related to diagnosis and death)
- Emergency department visits in the last 30 days of life
- ICU admissions in the last 30 days of life
- Hospitalization in the last 30 days of life (number of hospitalizations, reasons for hospitalizations)
- Use of life-sustaining treatments (e.g., mechanical ventilation, vasopressors,

- tracheostomy, dialysis for acute kidney injury, percutaneous endoscopic gastrostomy) in the last 30 days of life
- Transfusion in the last 7 days of life
- Place of death (home, hospital, facility, etc.)
- Inpatient mortality rate

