Models for comparison with historical control: For AML and MDS specifically, we will compare outcomes (EOL quality indicators) to a historical control cohort, which we have previously collected and published.¹² Rates of EOL outcomes in the historical cohort are shown in Figure 4, and range from <20% (chemotherapy in the last 14 days of life) to >80% (hospitalization in the last 30 days of life). Rates of EOL outcomes in this study population will be graphically summarized in a similar fashion. We aim to compare EOL outcome measures in this study population to EOL outcomes seen in the historical cohort referenced above.

Figure 1: End of life quality indicators (2014-2019)

Version Date: 5/10/23

PRMC#: UOCPC22039

Study Protocol

ClickIRB #: STUDY00007403

Qualitative analyses: All inpatient ACP visits and interviews will be audio-recorded by study personnel and then transcribed by a professional transcription service. Inpatient ACP visit transcript themes will focus on the APPs/hematology/oncology fellows ability to assess EOL concerns brought up by the patient and caregiver, as well as advance directive completion. Post-intervention interview themes will focus on participant experience during the inpatient ACP visit and feedback which will be used to further optimize the study procedures and intervention.

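### The historical end-of-life comparison in section 8.2.2 aligns the groups by disease only: AML/MDS study patients aged 60+ and enrolled as inpatients are set against a cohort described only as adults

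*Combined protocol and SAP*

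**What the plan says.** Section 1.6 sets the objective of assessing preliminary efficacy in older patients in a single-arm study, with a historical control as the comparator. Section 2.3 hypothesizes better completion of advance directives and better end-of-life (EOL) care.

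The comparison is in section 8.2.2: "For AML and MDS specifically, we will compare outcomes (EOL quality indicators) to a historical control cohort, which we have previously collected and published". It gives historical rates from below 20% (chemotherapy in the last 14 days of life) to above 80% (hospitalization in the last 30 days). It plans a similar graph for the study population and states an aim to compare the two. The paragraph is headed as models for comparison, but no model follows. The figure caption dates the cohort 2014-2019.

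Who is in each group:

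- Study, section 3.9: "We will recruit patients with hematologic malignancies aged 60 and above".
- Study, section 3.5: "Being managed in the inpatient setting", plus ability to consent.
- Historical cohort, section 1.3: "among adults with AML and myelodysplastic syndrome (MDS) seen at the Wilmot Cancer Institute (WCI) and its affiliated community centers".

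On data collection, section 7.2.2 says of the EOL indicators: "We have previously collected this information in a retrospective fashion and will use similar procedures to extract this information prospectively from the medical records".

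**The concern.** This is the only between-group comparison planned for the EOL part of the hypothesis. As written, it sets patients aged 60+, enrolled during an admission and able to consent, against a cohort described as all adults, inpatient or not. If use of intensive care, life support, hospice or chemotherapy near death varies with age, or with who reaches an admission in a state to consent, the rates would differ even if the advance care planning (ACP) visit changed nothing. The planned graph gives a reader no way to tell the two explanations apart.

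A second question is which study decedents are counted. Section 3.11 excludes adults who lose capacity to consent during the study, while section 7.1 follows patients through the medical record until death or for up to 5 years. If the first rule were applied to the EOL analysis, patients who lose capacity, who may be among the sickest, would drop out of the study side only.

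**Working it through.** **1. The groups side by side.** The documents give no sample size, power or planned difference for this comparison, so there is no figure of the plan to reproduce.

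| Feature | Study (3.5, 3.9) | Historical cohort (1.3, 8.2.2) | Aligned in 8.2.2? |
|---|---|---|---|
| Disease | AML/MDS subset | AML/MDS | Yes |
| Age | 60+ | adults | No |
| Setting at entry | inpatient | seen at center or affiliates | No |
| Capacity to consent | required | not stated | No |
| Period | current study | 2014-2019 | No |
| Indicator windows | mostly counted back from death (7.2.2) | similar extraction (7.2.2) | Largely |

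The mismatch lies in who is included, not in how the indicators are defined.

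**2. Age mix.** With s the under-60 share of historical decedents and D the rate difference between under-60s and 60+, the all-adult rate differs from the 60+ rate by s × D. Neither is given. Assuming s = 10-30% and D = 10 points, the shift is 0.10 × 10 = 1 point to 0.30 × 10 = 3 points, of unknown sign. Other assumed values scale it in proportion.

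**3. Early deaths.** A study patient who dies during the index stay, or within 30 days of it, meets the 30-day hospitalization indicator by eligibility. Let f be the share of study decedents who do so. Assume exponential survival with median m = 6 or 12 months (the older-AML range in the background section; no MDS median is given), deaths counted to 5 years (7.1), and L further days of index stay after entry (assumed). Then

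F(d) = 1 - 2^(-d/(30.44 m)), f = F(L + 30)/F(5 years).

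F(5 years) is 0.999 for m = 6 and 0.969 for m = 12.

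| L (days) | f, m = 12 | f, m = 6 | f × (1 - 0.80), points |
|---|---|---|---|
| 0 | 5.7% | 10.8% | 1.1 to 2.2 |
| 14 | 8.3% | 15.4% | 1.7 to 3.1 |
| 28 | 10.8% | 19.8% | 2.2 to 4.0 |

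The last column takes 80% as the rate that would otherwise apply. The figures are not bounds. Patients enrolled while hospitalized may have a higher early hazard, which raises f. The plan's rate is above 80%, and historical deaths also follow admissions, which lowers the excess.

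**4. Sampling error.** The number of AML/MDS study deaths is not given; 10 and 20 are assumed out of 50 patients with any hematologic malignancy. Exact (Clopper-Pearson) 95% intervals at an observed 80% are:

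- 8/10: 44.4-97.5%
- 16/20: 56.3-94.3%

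**5. Precision cost of restricting by age.** The size of the historical cohort is not given. Assume that restriction cuts it from 300 to 100 decedents, with 80% in both groups. Newcombe 95% intervals for study minus historical, in points, are:

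| Study deaths | 300 historical | 100 historical |
|---|---|---|
| 16/20 | -22.0 to +12.9 (width 34.9) | -22.6 to +14.9 (width 37.5) |
| 8/10 | -31.3 to +15.1 (width 46.4) | -31.7 to +16.9 (width 48.6) |

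Study deaths dominate the variance, so a loss of two thirds of the historical decedents adds only 2.6 or 2.2 points of width.

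**The case against.** The best reply is that the cohort was published and its paper is not before us. Section 1.3 is a background sentence, not an eligibility statement, and the cohort may already be older or mostly hospitalized. This stands in part. What the documents show is an unrestricted comparison with a cohort whose criteria they do not state. The citation does not settle it: sections 1.3 and 8.2.2 cite reference 12, section 1.6 cites 13, and the AML/MDS end-of-life paper is item 13 in the list. That slip is editorial, since the title identifies the paper.

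A second reply is that the comparison is descriptive and any bias is likely to be lost in intervals 35 to 49 points wide. That limits the severity, but it does not remove the reason to apply the study's own age floor. Section 8.2.2 promises exact intervals for rates in its feasibility paragraph, but none for the difference from the historical cohort.

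A reader might go further and require at least one admission after diagnosis in the historical group. The documents do not support this. Every decedent hospitalized in the last 30 days has such an admission, so the filter conditions on the outcome: it can remove only decedents who were not hospitalized then, and can only raise the historical rate. If a share h had no admission, the rate moves from p to p/(1 - h). At p = 80% that is +1.6 points for h = 2%, +4.2 for 5% and +8.9 for 10% (h assumed). Section 7.2.2 also lists hospitalization only for the last 30 days of life, so any-time admissions are not shown to be held.

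Dropping early deaths from the study group alone is equally tempting, and one-sided. With an 80% study rate, removing f = 10.8-19.8% (all hospitalized) gives (0.80 - f)/(1 - f), a fall of 2.4 to 4.9 points against an unchanged historical bar.

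**Conclusion.** The concern holds in a limited form. Section 8.2.2 aligns the groups by disease only, although the stated target is older patients and the study enrolls only inpatients aged 60+ who can consent. A difference in EOL rates can therefore reflect age mix and selection as well as care.

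The size and direction are not established. The illustrations (1-3 points for age mix, 1.1-4.0 points for early deaths on one indicator) rest on assumed values, should not be added together, and do not show that the bias is small. Sampling error is probably larger at 10 to 20 study deaths. A reader might infer that the comparison favors the intervention, favors the control or is invalid. The documents support none of these: no test is planned, the selection effects can run either way, and the cohort's own criteria are not reported here. This is a cheap improvement to a secondary, descriptive analysis, and feasibility is untouched.

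**What to change.** In section 8.2.2:

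1. Make the comparison against historical AML/MDS decedents aged 60+, the study's own age floor, or state that the cohort already meets it. Show the full cohort for reference only, and cite it consistently.
2. State that all consented AML/MDS decedents are analyzed, with or without an ACP visit, and that loss of capacity after consent (3.11) does not remove a patient from the record-based EOL analysis (7.1) where consent allows.
3. Report study-minus-historical rate differences with 95% intervals, labelled descriptive.
4. Note beside the graph that inpatient entry, survival to consent, capacity and calendar period are not matched, and that study patients who die in or within 30 days of the index stay meet the 30-day hospitalization indicator by eligibility.

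Do not add an admission filter or a study-only exclusion of early deaths.

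The cost is a few sentences and an age filter on data that the team reports having collected. The downside is fewer historical decedents and slightly wider intervals, for example 34.9 to 37.5 points at 20 study deaths under the assumptions above. Differences in setting, capacity and period remain and can only be disclosed.
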